**Insulin Only Bionic Pancreas
Bridging Trial
Adult RCT Phase**

Statistical Analyses Plan

Version 0.4

September 21, 2018

Based on Protocol Version 8.0

Note: The table shells are included in a separate document

1 **Version History**

2

Version	Author	Approvers	Effective Date	Revision Description	Study Stage
1.0	[name]/ [name]	[name] [name] [name] [name]	9/xx/2018	Original Version	The Adult RCT Phase started the enrollment on 7/xx/2018. Still enrolling

3

4 **Lead Statistician and Author:**

5 _____

6

7 **Senior Statistician Approver:**

8 _____

9

10 **JAEB PI Approver:**

11 _____

12

13 **Sponsor Approver:**

14 _____

15

16 **Study PI Approver:**

17 _____

18

19 **1. Study Overview**

20 This document outlines the statistical analyses to be performed for the IOBP Bridging Trial – Adult RCT
21 Period - to be presented to DSMB and maybe published.

22
23 The IOBP Bridging Trial consists of four different periods in this order:

- 24 - Test Run,
- 25 - Adult RCT,
- 26 - Pediatric Transitional,
- 27 - Pediatric RCT.

28
29 The Test-Run Period will be completed and the data will be reviewed to verify safety prior to beginning
30 the Adult RCT Period.

31
32 The Adult RCT Period will consist of a multi-center, three-period, random-order, cross-over, feasibility
33 study in 36 adult participants ≥ 18 years old with T1D (18 participants at MGH and 18 participants at
34 Stanford). All 18 adult participants at MGH will have a Senseonics Eversense CGM sensor implanted prior
35 to the initiation of the Adult RCT Period by the clinical PI at MGH ([name]) or by a study
36 physician under his supervision. These subjects will use the Senseonics Eversense CGM as the input to the
37 bionic pancreas instead of the Dexcom G5. All 18 adult participants at Stanford will use the Dexcom G5
38 CGM as the input to the bionic pancreas. All other aspects will remain the same across the two sites.

39 Insulin therapy for each participant will be administered (i) in one period using the iLet in the insulin-only
40 configuration with the iLet pigtail adapter and the iLet ready-to-fill insulin cartridge, the Contact Detach
41 infusion set, and the insulin analog that they use for their usual care (either Humalog or Novolog), (ii) in
42 another period using the iLet in the insulin-only configuration using the iLet pigtail adapter, the Contact

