 - 72 ○ Approximately 9 participants in a young adult group (18–24 years old)
 - 73 ○ Approximately 27 participants in an adult group (\geq 25 years old)
- 74 • At least 3 daily SMBG or 2 if used with a CGM

75

76 The following table gives an overview of the schedule of study visits and key procedures during each one
 77 of the three 7-day randomized treatment periods [BP with analog insulin (1), BP with rapid insulin (2),
 78 and UC (3)]:

	Screening	Senseonics Eversense Sensor Insertion	Each Treatment Period			Senseonics Eversense Sensor Removal
			0	Day 3 or Day 4	Day 7	
Informed Consent	X					
Eligibility assessment	X		X			
Bloodwork: eGFR and HbA1c	X					
EKG	X					
Body weight	X		X		X	
Urine pregnancy test	X					
Physical exam	X					
Insertion of Dexcom CGM sensor			X			
Insertion of Senseonics Eversense CGM sensor		X				
Removal of Senseonics Eversense CGM sensor						X
Psychosocial questionnaires			X		X	
Data download					X	
Adverse event querying			X	X	X	

79

80 **2. Statistical Hypotheses**

81 The primary outcome for this study is CGM-measured mean glucose when compared during (2) BP with
82 rapid insulin and UC (3) treatment periods.

83 The hypotheses are:

- 84 1. *Null Hypothesis*: There is no difference in mean CGM-measured glucose during UC and BP with
85 rapid insulin treatment periods
- 86 2. *Alternative Hypothesis*: The mean CGM-measured glucose is different during UC and BP with
87 rapid insulin treatment periods.

88

89 The intervention will be considered effective if the above null hypothesis is rejected using a significance
90 level of 0.05 (i.e. $p < 0.05$).

91

92 **3. Sample Size**

93 Thirty-six subjects will be enrolled and randomized at two sites. This is a convenience sample; however
94 assuming an effective SD of 25 mg/dl for mean glucose, the half width of the associated 95% confidence
95 interval are approximately ± 10 mg/dl for $N=36$ and ± 15 mg/dl for $N=18$. Results from the control period
96 of the JDRF CGM RCT were used to estimate SD for mean glucose in the proposed study.

97

98 **4. Outcome Measures**

99 **4.1 Primary Efficacy Outcome**

- 100 • CGM-measured mean glucose

101

102 **4.2 Secondary Efficacy Outcome**

103

104 **4.2.1 Secondary Efficacy Endpoint Included in Hierarchical Analysis**

- 105 • CGM-measured time < 54 mg/dl

106

107 **4.2.2 Other Secondary Efficacy Outcomes**

108 The following endpoints are considered exploratory.

- 109 • CGM metrics related to hypoglycemia

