- 168 • Safety outcomes will be reported for all enrolled participants, irrespective of whether the safety
169 event happened during the randomized treatment periods or in between (i.e. during wash-out
170 periods).
- 171

172 Sensitivity Analyses:

- 173 • Primary and secondary CGM-based outcomes will be replicated using:
 - 174 ○ all CGM data during the randomized treatment periods (i.e. days 1-7), and
 - 175 ○ only the first 24hr of CGM data from each treatment period following randomization.
 - 176 • Additional models for primary and secondary outcomes will be run to test for any carry-over
177 effects, by adding a treatment by order interaction term.
- 178

179

180 **6. Primary Analysis**

181 The primary analysis will be a comparison of CGM-measured mean glucose between (2) BP with rapid
182 insulin versus (3) UC treatment periods.

183

184 Plots and summary statistics appropriate to the distribution for mean glucose will be reported.

185

186 A repeated measures linear model with mean glucose as the dependent variable will be fit to the data
187 including all three treatment periods. The model will adjust for treatment period and account for
188 correlated data from the same subject using an unstructured covariance matrix.

189

190 The p-value for the primary analysis will be calculated using a contrast in the model described above
191 between the (2) BP with rapid insulin (3) UC treatment arms. From prior experience, the values for mean
192 glucose will follow a bell-shaped distribution. Residual values will be examined for an approximate normal
193 distribution. If values are highly skewed then rank transformation will be used instead.

194

195 **7. Secondary Analyses**

196 Plots and summary statistics appropriate to the distribution will be given for both mean glucose and time
197 below 54 mg/dl for all three treatment arms.

198

199 For mean glucose, contrasts from the same model described above will also be used to compare:

- 200 • (2) BP with analog insulin versus (3) UC, and
- 201 • (2) BP with rapid versus (1) BP with analog insulin

202 Both of these are considered secondary analyses.

203

204 A similar model will be fit with time below 54 mg/dl as the dependent variable with contrasts for all
205 three pairwise comparisons of the treatment arms. It is anticipated that the distribution of this metric will
206 be skewed. In this case, a transformation will be used as described above.

207

208 **7.1 Hierarchical Analyses**

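### The 95% half-widths of ±10 and ±15 mg/dl in SAP Section 3 do not follow from the SD of 25 mg/dl printed with them, which gives ±8.5 and ±12.4

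*SAP*

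**What the plan says.** Section 3 (Sample Size) fixes the size first: "Thirty-six subjects will be enrolled and randomized at two sites". It offers no power calculation ("This is a convenience sample; however") and gives expected precision in its place: "assuming an effective SD of 25 mg/dl for mean glucose, the half width of the associated 95% confidence" interval is put at approximately ±10 mg/dl for N=36 and ±15 mg/dl for N=18. The SD is said to come from the control period of an earlier randomised CGM trial. No correlation, dropout allowance, assurance level or rounding rule is given. The section does not say whether 25 mg/dl describes one treatment period or a difference between two.

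Section 1 describes the design: "The Adult RCT Period will consist of a multi-center, three-period, random-order, cross-over, feasibility" study. Section 6 obtains the primary result from a model that handles "correlated data from the same subject using an unstructured covariance matrix", and states: "The p-value for the primary analysis will be calculated using a contrast in the model described above", between BP with rapid insulin and usual care. The quantity of interest is thus a within-participant difference.

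**The concern.** A half-width for a mean depends on the SD, the number of participants and the confidence level. All three are printed in the sentence, and together they give smaller half-widths than the two stated.

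Because there is no power target, these half-widths are the SAP's only numerical statement of what 36 participants, or a half-sample of 18, can show. Eighteen is the size of each site and of each usual-therapy group (injections or pump) in Section 1. A reader cannot tell whether the SD or the half-widths are wrong. If 25 is the SD of the within-participant difference, the plan understates its precision. If 25 is the SD of one period, the printed figures may be too narrow, right or too wide, depending on a correlation that is not given.

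**Working it through.** **Inputs (SAP Section 3).** SD = 25 mg/dl; 95% two-sided interval; N = 36 and N = 18; stated half-widths about 10 and 15 mg/dl.

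**1. Attempt to reproduce the stated figures.** Half-width = t(0.975, N−1) × SD / √N.

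- N = 36: 2.0301 × 25 / 6 = 8.46
- N = 18: 2.1098 × 25 / √18 = 12.43

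The normal quantile gives 8.17 and 11.55. Degrees of freedom of N−2 give 8.47 and 12.49. None of these is 10 and 15.

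**2. Size of the gap.** 10 / 8.46 = 1.18 and 15 / 12.43 = 1.21. The differences are 10 − 8.46 = 1.5 and 15 − 12.43 = 2.6 mg/dl.

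**3. SD implied by the stated figures.** SD = half-width × √N / t.

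- 10 at N = 36: 10 × 6 / 2.0301 = 29.56
- 15 at N = 18: 15 × √18 / 2.1098 = 30.16

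Both point to about 30, and an SD of 30 gives 10.15 and 14.92. Allowing for rounding to the whole mg/dl, 9.5 to 10.5 at N = 36 needs an SD of 28.08 to 31.03, and 14.5 to 15.5 at N = 18 needs 29.16 to 31.17. Under this formula both hold only for an SD of 29.16 to 31.03. The printed 25 lies outside that range.

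**4. If 25 is the SD of one period (assumption).** With correlation rho between two periods in the same person, SD of the difference = 25 × √(2(1 − rho)).

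| rho (assumed) | SD of difference | N = 36 | N = 18 |
|---|---|---|---|
| 0 | 35.36 | 11.96 | 17.58 |
| 0.3 | 29.58 | 10.01 | 14.71 |
| 0.5 | 25.00 | 8.46 | 12.43 |
| 0.7 | 19.36 | 6.55 | 9.63 |

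The SD range in step 3 corresponds to rho = 1 − SD² / (2 × 25²), that is, 0.23 to 0.32.

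**5. Other readings with SD 25.**

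| Reading | N = 36 | N = 18 |
|---|---|---|
| 90% interval | 7.04 | 10.25 |
| 99% interval | 11.35 | 17.08 |
| Two groups of N/2 | 16.94 | 24.98 |
| Two groups of N each | 11.75 | 16.94 |
| Bonferroni for three comparisons | 10.48 | 15.64 |
| Half-width not exceeded with 90% assurance | 9.70 | 15.01 |

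The assurance reading matches both figures to the whole mg/dl, and Bonferroni comes close. Section 3 mentions neither.

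**6. Rounding.** To the nearest 5, 8.46 and 12.43 become 10 and 10. Rounding both up to the next 5 gives 10 and 15.

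**The case against.** The best defence is that the figures are labelled approximate, both are multiples of 5, and the SD may itself be rounded. The N = 18 value misses the 12.5 cut-off by only 0.07. An unrounded SD of 25.14 to 25.49 would print as 25 and give about 8.5 to 8.6 and 12.5 to 12.7, which round to 10 and 15 to the nearest 5. So would the loss of one participant per row (8.59 at N = 35, 12.85 at N = 17). A per-period SD of 25 with a correlation near 0.3 gives 10.0 and 14.7, and a control-period source for the SD is compatible with that reading. Ninety per cent assurance also works. Finally, the sentence does not say that the interval is for the difference between arms, and no decision rests on it.

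These calculations are correct, and they show that the cause cannot be identified from the SAP. A rounding convention, in particular, cannot be ruled out. But each explanation brings in an input that Section 3 does not state. If coarse rounding is the cause, it turned 12.4 into 15, a 21% change in a figure whose only purpose is to convey precision. The argument about consequences stands in full: the sample size and the tests are unaffected, and on the direct reading the error is conservative.

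**Conclusion.** The concern holds. The half-widths in Section 3 do not follow from the SD, confidence level and sample sizes in the same sentence. The direct calculation gives ±8.5 mg/dl (N = 36) and ±12.4 mg/dl (N = 18), so the printed values are 18% and 21% too wide. This takes 25 mg/dl as the SD of the quantity being estimated, with complete data and N−1 degrees of freedom. If 25 is instead a per-period SD, correlations from 0 to 0.7 give half-widths for the difference from 12.0 down to 6.6 (N = 36) and from 17.6 down to 9.6 (N = 18). The printed pair is then right only for a correlation of about 0.23 to 0.32. It is an arithmetic inconsistency that should be corrected. It does not affect the trial's size, its tests or their validity.

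**What to change.** Rewrite the one sentence in Section 3 so that the SD and the half-widths agree, and say that they refer to the difference in mean glucose between BP with rapid insulin and usual care. The sponsor's original calculation decides which version applies:

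- If 25 mg/dl is the SD of the within-participant difference, print ±8.5 (N = 36) and ±12.4 (N = 18).
- If the SD of the difference used was about 30, correct the SD and keep ±10 and ±15.
- If 25 mg/dl is a per-period SD, say so and give the within-person correlation used.
- If the half-widths were rounded to a multiple of 5, print the unrounded values. If an assurance level or another allowance was applied, state it.

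The cost is one corrected sentence, with no extra participants and no change to any analysis.

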- All sensor data excluding the first 48 hours will be included in the calculation of glycemic metrics.
 - Only subjects with at least 24hr of CGM data in any two of the three treatments periods will be included in CGM analyses. It is considered that 24hr of data is the minimum and a representative amount of data for any treatment period.
 - If there are 12-<24hr of CGM data from days 3-7 in each one of the three treatment periods and there are more CGM data during days 1-2, then the data from days 3-7 will be supplemented with
- 136

- 137 data from days 1-2 (going backwards) until 24hr of data is reached. Otherwise the data are
138 considered missing for that treatment period.
- 139 • Metrics will be calculated giving equal weight to each CGM point from each treatment period.
- 140

141 **5. Description of Statistical Methods**

142 **5.1. General Approach**

143 Analyses will involve pairwise comparisons of the three treatment arms:

- 144 1. Bionic Pancreas (BP) with analog insulin
 - 145 2. Bionic Pancreas (BP) with rapid insulin
 - 146 3. Usual Care (UC)
- 147

148 All primary, hierarchical, and secondary analyses comparing the three treatment periods will follow the
149 intention-to-treat (ITT) principle with each period analyzed according to the treatment assigned by
150 randomization. All randomized participants with at least 24hr of CGM readings during at least two of the
151 three treatment periods will be included in the primary, hierarchical, and secondary analyses of CGM
152 metrics. There will be no imputation of missing data.

153 All p-values will be two-sided.

154 Standard residual diagnostics will be performed for all analyses. If values are highly skewed, then a rank
155 transformation will be used instead for the primary and secondary outcomes. From prior experience, the
156 values for time <54 mg/dl will have a skewed distribution and for mean glucose a bell-shaped
157 distribution.

158

159 **5.2. Analyses Cohorts**

160 Primary and Secondary Analyses:

- 161 • For CGM-based and insulin outcomes, all randomized participants and treatment periods will be
162 analyzed according to the ITT principle and the 24hr rule as described above.
 - 163 • For questionnaires, all questionnaires with at least one item answered will be included in
164 analyses. Total and subscale score may be calculated or not depending on specific instructions or
165 rules (see section 7.2).
- 166

167 Safety Analyses:

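### The two-of-three-period rule removes randomised participants with exactly one valid CGM period from an analysis labelled ITT, although the planned model can use that period; under arm-dependent dropout this can bias the primary contrast slightly

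*SAP*

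**What the plan says.** Section 5.1 states that the primary, hierarchical and secondary comparisons follow the "intention-to-treat (ITT) principle with each period analyzed according to the treatment assigned by" randomization. The next sentence sets the entry condition for CGM metrics: "All randomized participants with at least 24hr of CGM readings during at least two of the" three treatment periods. Section 4.3 states the same condition as an exclusion, and Section 5.2 applies the ITT principle and the 24-hour rule together to all randomised participants. Section 5.1 also rules out imputation of missing data.

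Section 4.3 describes 24 hours as both the minimum and a representative amount of data for a treatment period.

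The primary model (Section 6) is a repeated measures linear model fitted to all three treatment periods, accounting for "correlated data from the same subject using an unstructured covariance matrix".

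The sensitivity analyses in Section 5.2 change the CGM window (days 1-7, or the first 24 hours) or test for carry-over. None is stated to lift the two-period condition. Section 10 plans a participant flow chart and a listing of dropouts with reasons. No dropout rate is assumed anywhere.

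**The concern.** Having two valid periods is a condition met or failed after randomisation. A participant who completes one period with adequate CGM data and then leaves has been randomised, treated as assigned and observed, yet contributes nothing. The plan regards the deleted period as representative.

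The model does not need the exclusion. A likelihood fit with unstructured covariance accepts participants with one, two or three observed periods. The plan already relies on this for incomplete participants: someone with both BP periods and no UC period is kept, although they give no direct within-person BP versus UC difference.

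At stake is the BP-rapid versus UC estimate. If participants leave because a first BP period went badly, the rule deletes that poor period and leaves a more favourable BP sample. The primary test also opens the hierarchy of five further tests in Section 7.1.

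**Working it through.** **Inputs from the SAP.** N = 36 (Section 3: "Thirty-six subjects will be enrolled and randomized at two sites"), SD 25 mg/dl for mean glucose (Section 3), three treatment periods, two-sided 5% level.

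**Assumptions, not in the SAP.** Within-subject correlation ρ of 0.3, 0.5 or 0.7; balanced order, so one third start on each treatment; no period effect; those who leave do so after period 1 with a usable first period.

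**The plan's own figure.** Section 3 gives 95% half widths of about ±10 mg/dl (N = 36) and ±15 mg/dl (N = 18). From SD 25:
- N = 36: 2.030 × 25/√36 = 8.5
- N = 18: 2.110 × 25/√18 = 12.4

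The stated values would need an SD of about 30. They do not depend on the two-period rule, so this discrepancy is separate from the present point.

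**Bias under the SAP rule.** Suppose a fraction p with the highest glucose leave among those who start on either BP treatment. The share leaving is 2p/3. Let z be the mean standardised value in the top fraction p.
- Leavers who started on BP-rapid lie z × 25 above the BP-rapid mean and, in expectation, ρ × z × 25 above the UC mean.
- Leavers who started on BP-analog lie ρ × z × 25 above both means, so their effect on the contrast cancels.

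Hence, for BP-rapid minus UC after exclusion,

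bias = -[(p/3)/(1 - 2p/3)] × z × 25 × (1 - ρ), and SE = √[2 × 25² × (1 - ρ)/n], with n = 36 × (1 - 2p/3).

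| p | z | leavers | ρ | bias (mg/dl) | SE | bias/SE |
|---|---|---|---|---|---|---|
| 0.10 | 1.755 | 2.4 | 0.3 | -1.10 | 5.10 | 0.21 |
| 0.10 | 1.755 | 2.4 | 0.5 | -0.78 | 4.31 | 0.18 |
| 0.10 | 1.755 | 2.4 | 0.7 | -0.47 | 3.34 | 0.14 |
| 0.20 | 1.400 | 4.8 | 0.3 | -1.88 | 5.30 | 0.36 |
| 0.20 | 1.400 | 4.8 | 0.5 | -1.35 | 4.48 | 0.30 |
| 0.20 | 1.400 | 4.8 | 0.7 | -0.81 | 3.47 | 0.23 |

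Example (p = 0.20, ρ = 0.3): (0.0667/0.8667) × 1.400 × 25 × 0.7 = 1.88. Separate simulations of this mechanism gave -0.45 to -1.92 and about -0.3 to -1.8 mg/dl, hence the overall range of -0.3 to -1.9. With one-period participants kept, the bias was about 0.

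**Other mechanisms** (simulation at N = 36, maximum likelihood, unstructured covariance):

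| Who leaves after period 1 | Bias, excluded | Bias, kept |
|---|---|---|
| BP starters, probability rising with glucose | -0.40 to -0.98 | 0.04 to 0.07 |
| 80% of the top quartile on BP-rapid | -0.61 to -1.47 | 0.08 to 0.15 |
| Any arm, probability rising with absolute glucose | +0.21 to +0.49 | 0.00 to 0.03 |

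The Monte Carlo standard error, given for the kept column, is 0.09 to 0.14. If the top 20% relative to each arm's own mean leave from any arm, UC starters contribute an equal and opposite term and the bias cancels. Dropout unrelated to glucose gave zero bias under both approaches (simulated at N = 3600).

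**Type I error.** A shift of d standard errors gives Φ(-1.96 + d) + Φ(-1.96 - d). For d = 0.14 this is 5.2%; for d = 0.36 it is 6.5%.

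**Precision.** With 2, 4 or 6 one-period participants spread evenly over the treatments and the rest complete, keeping them multiplies the SE by 0.977 to 0.997, a reduction of 0.3% to 2.3%.

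**The case against.** The rule is open, prespecified and neutral between arms, and Sections 4.3, 5.1 and 5.2 state it consistently. Section 5.1 explains ITT as analysing each period under its assigned treatment, which the rule does not breach. The flow chart and dropout listing would make any exclusion visible. Requiring any two periods also has a rationale: each included participant then supplies a within-person comparison for at least one of the three planned contrasts. All of this stands. The matter is one of a modified ITT set carrying the ITT label, not of a concealed exclusion.

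A reader might infer that the rule does bias the primary result, and towards BP. The SAP does not support that. It gives no dropout rate, the treatment periods last only 7 days, and nothing in it suggests that poor glucose on BP will drive people out. Bias requires one-period participants, and loss that depends on glucose differently by arm. High absolute glucose in any arm gives a small bias against BP.

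A reader might also infer that the model could recover everyone with fewer than two valid periods. It cannot: a participant with no valid period contributes nothing without imputation. Because Section 4.3 sets aside the first 48 hours and then requires 24 hours of data, someone who stops early in the first period will generally have no valid period and stays out either way.

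Finally, the calculations concern mean glucose, not the rank-transformed analysis that the SAP anticipates for time below 54 mg/dl.

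**Conclusion.** The point holds as a minor one. The plan applies the ITT label to a set that leaves out participants with exactly one valid period, does so without need given its own model, and provides no analysis to check the effect.

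The possible bias in BP-rapid minus UC is roughly -0.3 to -1.9 mg/dl, about 0.1 to 0.4 standard errors. This rests on SD 25 mg/dl, correlation 0.3 to 0.7, N = 36 and about 2 to 5 high-glucose dropouts confined to those starting on BP. Direction and size depend on the mechanism. The bias is zero when loss is unrelated to glucose, and the result is unchanged when nobody has exactly one valid period. Keeping the observed period removes the bias when dropout depends on observed data; it does not protect against dropout driven by unobserved values. The gain in precision is too small to be a reason by itself.

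**What to change.** In Sections 4.3, 5.1 and 5.2, admit to the primary model every treatment period with at least 24 hours of CGM data, whatever the participant's number of valid periods. State that the model is fitted by likelihood and that participants with no valid period cannot contribute. Keep the two-of-three-period set as a sensitivity analysis in Section 5.2. Consider the same change to the two-of-three condition for daytime and nighttime data in Section 7.2.

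The cost is SAP wording and one extra sensitivity analysis; the model and data collection do not change. The SAP's version history records the adult phase as still enrolling, so the change could be made at that stage before results are known.

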 - 110 ○ % < 70 mg/dL
 - 111 ○ % < 60 mg/dL
 - 112 ○ low blood glucose index
- 113 • CGM metrics related to overall control
 - 114 ○ % time in target range 70-180 mg/dL
 - 115 ○ % time in target range 70-120 mg/dL
 - 116 ○ glucose variability measured with CV (coefficient of variation)
 - 117 ○ glucose variability measured with MODD (mean of daily difference)
- 118 • CGM metrics related to hyperglycemia
 - 119 ○ % > 180 mg/dL
 - 120 ○ % > 250 mg/dL
 - 121 ○ high blood glucose index

122
123
124
125
126
127

- Total daily dose of insulin
- Questionnaires - The following table provides a description of the questionnaires to be administered during each one of the three 7-day randomized treatment periods [BP with analog insulin (1), BP with rapid insulin (2), and UC (3)]:

Questionnaire's Name	Day 0	Day 7	Description
Diabetes Treatment Satisfaction Questionnaire - Status	X		Measures patient satisfaction with diabetes treatment. 8 items (6 for assessing treatment satisfaction and two for frequency of hypoglycemia and hyperglycemia). Scale 0-6. Higher scores denote higher satisfaction or higher frequency of hypoglycemia/hyperglycemia.
Diabetes Treatment Satisfaction Questionnaire - Change		X	Similar with the above (Status); except scale -3 to 3.
Diabetes Distress Scale	X	X	Measures Adult and Partner of Adult diabetes distress. Adult: 17 items (4 subscales and total score) and scale 1-6. Partner: 21 items (4 subscales and total score) and scale 0-4. Higher score denotes more of a problem or more distress.
Hypoglycemia Fear Survey	X	X	23 items (2 subscales and total score). Scale 0-4. Higher score denotes more fear.
Hypoglycemia Confidence Scale - Status	X	X	Measures confidence status. 8 items and a 4-level scale.
Hypoglycemia Confidence Scale - Change		X	Measures confidence change. 8 items and a 5-level scale.
INSPIRE Survey	X	X	Measures experience with automated insulin delivery systems. Adult and partner versions. 31 items. 5-point Likert scale.
Bionic Pancreas User Opinion Survey*		X	Measures user's experience with BP. 43 items. Two subscales (benefits and difficulties) and total score. 5-point Likert scale.
Daily At-Home Questionnaires			Administered at the end of each day – expected 6 times for each subject and randomized period combination. 17 items – most of them with sub-items (depending on the subject's answer).

128 *to be administered only during the two BP periods

129 **4.3 Calculation of CGM Metrics:**

- 130

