231 Regardless of the results of the hierarchical testing, summary statistics appropriate to the distribution will
 232 be tabulated.

233

234 **7.2 Other Endpoint Analyses**

235 CGM-Measured Outcomes

236 The analyses for the secondary CGM-measured outcomes will parallel the descriptive statistics and
 237 regression model mentioned above for the primary outcome without the hierarchical procedure.

238 Analyses will also be done limiting to daytime (6am-12mn) and nighttime (12mn-6am) data. Only
 239 subjects with at least 12hr of CGM data in any two of the three treatments periods will be included in
 240 daytime/nighttime CGM analyses.

241

242 Questionnaires

243 For each question, the percent of all answers will be reported across all subjects by treatment periods; and
244 if applicable, by beginning and ending of each treatment period. For questions with additional numeric or
245 ordinal scales, mean score will be reported in addition to the percent.

246
247 Some questionnaires will be administered at the beginning and ending of each treatment period, and the
248 results presented as such. If a subject completed the beginning but not the ending questionnaires, the
249 results will be presented as such (i.e. with different underlying number of subjects).

250
251 For some questionnaires total and subscale scores will be calculated and mean \pm SD values or percentiles
252 appropriate to the distribution will be reported across all subjects by treatment periods.

253
254 All questionnaires will be administered online (through REDCap) and subjects can skip specific
255 questionnaires or questions within a questionnaire. All questionnaires will be scored according to the
256 instructions given in the manual. In case no manual exists for a given questionnaire or the manual does
257 not provide guidance on how to handle missing questions, then the following “75% rule” will be used.
258 For all questionnaires, at least 75% of the questions must be completed to be included in the
259 analysis. This 75% rule will be applied separately for the total score and each subscale so it is possible
260 the sample size will be different for some subscales. The score used for analysis will be based on the
261 average among the questions that were answered and then scaled accordingly in order to a corresponding
262 total or subscale score.

263
264 The Daily At-Home Questionnaire will be administered at the end of each day (for a maximum of 6 times

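### Day 0 and Day 7 questionnaire summaries may rest on different participants, with no within-participant change specified, so the displayed difference can mix real change with a change in who is counted

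*SAP*

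**What the plan says.** The questionnaire table in SAP Section 4.2.2 marks four instruments for both Day 0 and Day 7 of each 7-day period: the Diabetes Distress Scale, the Hypoglycemia Fear Survey, the Hypoglycemia Confidence Scale - Status and INSPIRE.

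Section 7.2 (Questionnaires) then fixes how incomplete pairs are shown: "If a subject completed the beginning but not the ending questionnaires, the" ... "results will be presented as such (i.e. with different underlying number of subjects". Total and subscale scores, where calculated, are summarised by treatment period as mean and SD or as percentiles. No within-participant change and no summary restricted to participants with both forms is named.

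Three other rules bear on who is counted at each time:

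- Section 5.2 sets the entry condition form by form: "For questionnaires, all questionnaires with at least one item answered will be included in" the analyses. A Day 0/Day 7 pair is not required.
- Section 7.2 lets participants skip items or whole forms online. Where a manual gives no missing-item rule, a 75% completion rule applies separately to the total and to each subscale.
- Section 5.1 states, just after the CGM inclusion rule, "There will be no imputation of missing data".

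Section 7.2 also rules out formal hypothesis tests for questionnaires.

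**The concern.** A table with a Day 0 mean and a Day 7 mean for each treatment invites the reader to subtract one from the other. Under the stated rule, that difference has two parts: change in the people measured twice, and the effect of some people being present at Day 0 and absent at Day 7. The planned display does not separate them.

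Withdrawal is not needed for this to happen. A skipped Day 7 form, or a Day 7 subscale with too few items answered to be scored, has the same effect. The set of people may therefore also differ from one subscale to another.

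There is a smaller loss even with complete data. Separate means and SDs do not let a reader recover the SD or confidence interval of the change. The trial collects before-and-after pairs, and its CGM model in Section 6 accounts for correlation within a subject, but the questionnaire summaries make no use of the pairing.

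At stake is the reading of distress, fear, confidence and INSPIRE scores. As there is no model or test for these outcomes, the displayed summaries are the only evidence on them.

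**Working it through.** The SAP gives no questionnaire SD, effect size or expected missingness, so there is no stated figure to reproduce. What can be checked is the size of the artefact.

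**Inputs.** N = 36 (Section 3). k = number with Day 0 but no usable Day 7 in a given period (assumed). C and D = Day 0 means of those with both forms and of those lacking Day 7. d = (D - C)/SD (assumed).

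**Derivation, with nobody's score changing.**

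- Displayed Day 0 mean = [(N - k) x C + k x D]/N = C + (k/N) x (D - C)
- Displayed Day 7 mean = C
- Displayed Day 7 minus Day 0 = -(k/N) x (D - C), of size (k/N) x d in SD units
- Paired change among those with both = 0, for every k and d

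**In SD units**, for example 3/36 x 0.5 = 0.042 and 6/36 x 1 = 0.167:

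| k | d = 0.5 | d = 1.0 | d = 1.5 |
|---|---|---|---|
| 2 | 0.03 | 0.06 | 0.08 |
| 3 | 0.04 | 0.08 | 0.13 |
| 4 | 0.06 | 0.11 | 0.17 |
| 6 | 0.08 | 0.17 | 0.25 |

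**On a scale.** The Hypoglycemia Fear Survey has 23 items scored 0 to 4, so a summed total runs from 0 to 23 x 4 = 92, with higher meaning more fear. Assume Day 0 means of 30 (both forms) and 50 (Day 7 lacking):

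- k = 2: Day 0 mean = (34 x 30 + 2 x 50)/36 = 31.1; Day 7 mean = 30; apparent fall 1.1 points
- k = 4: (32 x 30 + 4 x 50)/36 = 32.2; apparent fall 2.2 points
- k = 6: (30 x 30 + 6 x 50)/36 = 33.3; apparent fall 3.3 points

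**Sign.** If those lacking Day 7 score worse at Day 0, the artefact looks like improvement. If they score better, it looks like worsening. If they do not differ (d = 0), it vanishes.

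**Yardstick.** The standard error of a 36-person mean is 1/sqrt(36) = 0.167 SD. The k = 6, d = 1 case equals one standard error; the k = 3, d = 0.5 case is a quarter of it.

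**What pairing does not remove.** Suppose completers do not change, while the k others worsen by e SD and then leave Day 7 blank. The true average change is (k/36) x e, but the paired summary still shows 0.

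**The case against.** The strongest reply is that this is a disclosed presentation choice on a low-stakes output. The SAP says openly that the numbers will differ. The outcomes are exploratory (Section 4.2.2), are not tested, and belong neither to the hierarchy in Section 7.1 nor to any false-discovery-rate category in Section 15. Section 10 adds a flow chart of subjects at all visits and a listing of dropouts with reasons. All of this is true and limits the weight of the point. But a differing N shows only that people are missing, not whether their Day 0 scores differed. The dropout listing carries no questionnaire scores and does not cover skipped forms.

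Second, change is not wholly unmeasured. The Hypoglycemia Confidence Scale - Change and the Diabetes Treatment Satisfaction Questionnaire - Change ask about change directly at Day 7. That stands, and it leaves distress, fear and INSPIRE as the main gap.

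Third, the table shells are a separate document. A paired column there cannot be excluded; the SAP text does not specify one.

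A reader might go further and infer that the rule favours the bionic pancreas, because dissatisfied participants or those in more demanding periods would be likelier to miss Day 7. The SAP does not support this. It gives no missingness by arm or by satisfaction. Burden felt during a period does not by itself worsen the score taken at Day 0, before that period's treatment. The direction is open.

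**Conclusion.** The point holds as a minor one. Section 7.2 lets Day 0 and Day 7 summaries rest on different people and names no within-participant change for the four instruments given on both days. The displayed difference can then shift by (k/36) x d SD with no true change, in either direction. That is about 0.04 SD for k = 3, d = 0.5 and 0.17 SD for k = 6, d = 1. Both k and d are assumptions, and if few Day 7 forms are missing the shift is small.

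No primary, hierarchical or error-controlled result is touched. The case for changing the plan is that a clearer summary is available from data already collected, not that a wrong conclusion is likely.

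**What to change.** For each scored questionnaire given on both days, add to Section 7.2 a summary by treatment period, among participants with both scores in that period, of:

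- Day 0 score, Day 7 score and within-participant change (mean, SD and 95% confidence interval, or percentiles if skewed);
- beside it, the number lacking a usable Day 7 score and their Day 0 scores.

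Apply this separately to the total and each subscale, since the scoring rule does. Keep the all-available summaries as a second table, and check the table shells for an existing paired column before adding one.

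The cost is a few sentences and some extra columns, with no new data or visits. The version history records enrolment as ongoing, so the summary could be specified in advance. The downside is that the paired table uses slightly fewer participants and describes completers only. It removes the artefact from changing participants but not bias from people who worsen and then do not complete Day 7, and a footnote should say so. The Day 0 comparison of those lacking Day 7 may rest on very few people and should be read as descriptive.
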